5.1.3 Subject Exclusion Criteria

The subject must be excluded from participating in the trial if the subject:

1. Subject is under the age of legal consent.
2. Female subject is pregnant, or has intended to become pregnant during the study, or is nursing.
3. Subject is mentally or legally incapacitated, has significant emotional problems at the time of pre-study (screening) visit or expected during the conduct of the study or has a history of a clinically significant psychiatric disorder over the last 5 years. Subjects who have had situational depression may be enrolled in the study at the discretion of the investigator.
4. Subject has received systemic antifungal therapy (oral, intravenous, or inhaled) within 30 days of study enrollment for reasons other than antifungal prophylaxis.
5. A subject has known (including a possible, probable, or proven fungal infection per EORTC/MSG version 2008 criteria) [8] or suspected invasive or systemic fungal infection at Baseline.
6. Subject has taken posaconazole within 10 days prior to study enrollment.

7. Subject has had major surgery, donated or lost 1 unit of blood (approximately 500 mL) or participated in another investigational study within 4 weeks prior to the pre-study (screening). The 4 week window will be derived from the date of the last study procedure (i.e. post-study, AE follow-up, etc.) in the previous study to the pre-study/screening visit of the current study.
8. Subject has had a history of Type I hypersensitivity or idiosyncratic reactions to azole agents.
9. Subject has a history of significant multiple and/or severe allergies (including latex allergy), or has had an anaphylactic reaction or significant intolerance to prescription or non-prescription drugs or food.
10. Subject has had moderate or severe liver dysfunction at baseline, in this protocol defined as aspartate aminotransferase (AST) or alanine aminotransferase (ALT) levels greater than three times the upper limit of normal (ULN), AND a total bilirubin level greater than two times the ULN.
11. Subject with chronic active hepatitis, cirrhosis, Hepatocellular Carcinoma (HCC), or other hepatic disease caused by virus.
12. Subject has had an ECG with a prolonged QTc interval by manual reading: QTc greater than 500 msec.
13. Excluded treatments prior to specific study phases. Subject has taken one of the following drugs listed in the [Table 1](#) below more recently than the indicated washout period prior to study treatment.

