14. Excluded treatments during the study treatment period. Subject has to take one of the following drugs that are listed in [Table 1](#) during the study.

Table 1 Prohibited Medications Prior to Start of Study Treatment and During Study Treatment

Prohibited Medications Prior to Start of Study Treatment and During Study Treatment	Washout Period ^a
Systemic antifungal therapy (oral, intravenous or inhaled) other than study drugs for reasons other than antifungal prophylaxis.	30 days
Investigational drugs (new chemical or biological entities): Investigational use of approved products or chemotherapy regimens may be permitted with the approval of the sponsor's project physician prior to use.	30 days
Prophylaxis of IFI with posaconazole.	10 days
Medications that are known to interact with azoles and may lead to life-threatening side effects: astemizole, cisapride, ebastine, halofantrine, pimozide, quinidine, and terfenadine.	10 days (astemizole) 24 hours (others)
Ergot alkaloids (ergotamine, dihydroergotamine or other licensed or investigational members of this class).	2 days
Medications known to lower the serum concentration/efficacy of azole antifungals: barbiturates, carbamazepine, cimetidine, isoniazid, phenytoin, rifabutin, rifampin, and St. John's Wort (hypericum perforatum).	24 hours
Prophylactic use of nonabsorbable antifungal drugs: Nasal sprays of amphotericin B and aerosolized amphotericin B are prohibited.	24 hours
HMG-CoA reductase inhibitors metabolized via CYP3A4 (eg, simvastatin, lovastatin, and atorvastatin).	24 hours
Cyclophosphamide ^b	24 hours

a: These waiting times should be observed prior to start of study treatment and during study treatment in subjects receiving a prohibited drug. No concurrent use is permitted. Deviations from these washout periods must be approved by the sponsor prior to use of study drug or prohibited agent.

b: Low dose cyclophosphamide use is allowed during the treatment period with a temporary interruption of study therapy on the day of cyclophosphamide dosing.

HMG-CoA=beta-hydroxy-beta-methylglutaryl-CoA; IFI = invasive fungal infection

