5.8 Subject Withdrawal/Discontinuation Criteria

Subjects may withdraw consent at any time for any reason or be dropped from the trial at the discretion of the investigator should any untoward effect occur. In addition, a subject may be withdrawn by the investigator or the Sponsor if enrollment into the trial is inappropriate, the trial plan is violated, or for administrative and/or other safety reasons. Specific details regarding discontinuation or withdrawal procedures; including specific details regarding withdrawal from Future Biomedical Research, are provided in Section 7.1.4 – Other Procedures.

Discontinuation from treatment is “permanent”. Once a subject is discontinued, he/she shall not be allowed to restart treatment.

A subject must be discontinued from the trial for any of the following reasons:

- The subject or legal representative (such as a parent or legal guardian) withdraws consent.
- Documentation of a fungal infection (proven, probable or possible IFI) according to the European Organization for Research and Treatment of Cancer/Invasive Fungal Infections and the National Institute of Allergy and Infectious Diseases Mycoses Study Group (EORTC-MSG version 2008) criteria [8];
- Subjects with a prolonged QTc interval on a manual measurement (QTc greater than 500 msec);
- A subject who, prior to start of study treatment and during study treatment, requires any of the prohibited medications listed in [Table 1](#) of Section 5.1.3.

- Inability to continue to take study medication according to schedule (See Section 5.2.2);
- Failure to comply with the dosing, evaluations, or other requirements of the study;
- A subject with liver function tests (ALT, AST, or total bilirubin) greater than 10 x ULN or other clinical or histopathologic evidence of drug-induced hepatotoxicity;
- A subject who has recovered from neutropenia ($ANC \geq 500/\text{mm}^3$) and has not considered risk factors of IFI remain at the discretion of investigator;
- The subject interrupts trial medication administration for more than 3 consecutive days;
- The subject has a medical condition or personal circumstance which, in the opinion of the investigator and/or Sponsor, places the subject at unnecessary risk through continued participation in the trial or does not allow the subject to adhere to the requirements of the protocol;
- The subject has a confirmed positive serum pregnancy test.

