7.1.1.5.2 Concomitant Medications

The investigator or qualified designee will record medication, if any, taken by the subject during the trial.

Nasal sprays of amphotericin B (AMB) and aerosolized AMB are prohibited during the Treatment Phase. Topical nonabsorbable antifungal agents may be used for the treatment of mucosal or cutaneous fungal infections. Any other antifungal therapy must be administered according to the following criteria. No other systemic antifungal therapy is allowed other than study treatment.

Investigational drugs (ie, other drugs not yet approved for marketing by the Food and Drug Administration [FDA] or local health authorities) are also prohibited during the treatment phase.

POS is a potent inhibitor of CYP3A4. Coadministration of POS with CYP3A4 substrates may result in large increases in exposure of CYP3A4 substrates. Caution is advised during co-administration of POS with CYP3A4 substrates and the dose of the CYP3A4 substrate may need to be reduced. Plasma concentrations of the CYP3A4 substrate and/or AEs should be closely monitored and the dose adjusted as needed.

Clinical and ECG monitoring (including QTc monitoring) is to be performed when the study drug is co-administered with one of the following drugs that have reported a potential risk of torsades de pointes: amiodarone, chlorpromazine, clarithromycin, domperidone, droperidol, levomethadyl, mesoridazine, methadone, erythromycin, sparfloxacin, and thioridazine.

The drugs listed below are permitted, although their efficacy and safety should be clinically monitored and/or serum levels followed with appropriate dosage adjustments as necessary at the initiation of study drug, periodically during treatment, and after discontinuation of study drug:

- Oral hypoglycemic agents
- Digoxin
- Coumadin-type anticoagulants
- Calcium channel blockers
- Theophylline
- Antiretroviral therapy (eg, efavirenz, atazanavir, or tenofovir).

Posaconazole interferes with the hepatic clearance of triazolam and midazolam, and thus, may enhance the sedative effects of these agents. Therefore, these agents are not allowed unless monitoring is provided for excessive sedation.

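### No interval is stated from the last posaconazole dose to a contraindicated CYP3A4 substrate, and Table 1 footnote a leaves unclear whether its 24 h or 2-day waits apply in that direction

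*Combined protocol and SAP*

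**What the plan says.** Exclusion 13 (section 5.1.3) keeps out a subject who has taken a Table 1 drug "more recently than the indicated washout period prior to study treatment". In that use the clock runs from the listed drug to posaconazole. The row for drugs with life-threatening azole interactions reads "10 days (astemizole) 24 hours (others"), where the others are cisapride, ebastine, halofantrine, pimozide, quinidine and terfenadine. Ergots have 2 days and statins metabolised via CYP3A4 have 24 h.

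Footnote a to Table 1 does three things. It says "These waiting times should be observed prior to start of study treatment and during study treatment in subjects receiving a prohibited drug". It bars concurrent use. It then says "Deviations from these washout periods must be approved by the sponsor prior to use of study drug or prohibited agent".

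Section 5.8 requires discontinuation of "A subject who, prior to start of study treatment and during study treatment, requires any of the prohibited medications listed in" Table 1. It makes discontinuation permanent but gives no interval after the last dose. The one washout set for posaconazole itself is at entry: "Subject has taken posaconazole within 10 days prior to study enrollment" (exclusion 6, repeated in Table 1). Section 7.1.1.5.2 states "POS is a potent inhibitor of CYP3A4".

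The oral suspension circular in section 12.10 contraindicates use with QT-prolonging CYP3A4 substrates (naming terfenadine, astemizole, cisapride, pimozide and quinidine), with CYP3A4 statins and with ergots. It gives no interval after stopping.

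**The concern.** For these drugs posaconazole is the inhibitor. A wait before posaconazole starts should depend on how fast the listed drug clears. A wait after posaconazole stops should depend on how fast posaconazole clears. Table 1 has one number per row. The split between astemizole and the rest of its row suggests that the numbers follow the listed drug; that is an inference, since the protocol does not say how they were chosen.

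Footnote a blurs this by mentioning treatment as well as entry, and use of the prohibited agent as well as of study drug. A site whose subject needs quinidine, or wants to resume simvastatin, after the last posaconazole dose will look for a figure, and the only one listed against those drugs is 24 h (2 days for an ergot). The hazards named in the circular are QTc prolongation with torsades de pointes, ergotism and rhabdomyolysis. By contrast, section 7.1.1.5.2 asks for monitoring of permitted interacting drugs, such as digoxin, after study drug stops; the contraindicated drugs have no matching instruction.

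**Working it through.** **Inputs.** Half-life about 30 h (section 4.2.2.1); mean 35 h, range 20-66 h (circular, Excretion; oral data, assumed to hold after IV dosing). IV dosing interval 24 h. Mean steady-state Cavg 1500 ng/mL (section 8.2.3.3, Table 5). Lower anchor for Cavg 500 ng/mL, because none of 49 earlier subjects at this dose fell below it (section 4.2.2). Mean oral Cavg 583 ng/mL in AML/MDS patients (circular, Table 11).

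**1. The plan's own figure.** Section 4.2.2.1 expects steady state in 6-8 days. With a 30 h half-life, the fraction of steady state reached is 1 - 0.5^(144/30) = 96.4% at 6 days and 1 - 0.5^(192/30) = 98.8% at 8 days. The figure reproduces.

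**2. Share left after the last dose**, one-compartment log-linear decline, 0.5^(hours/half-life). For example, 0.5^(24/30) = 0.574.

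| Half-life | 24 h | 48 h | 10 days |
|---|---|---|---|
| 20 h | 43.5% | 18.9% | 0.02% |
| 30 h | 57.4% | 33.0% | 0.4% |
| 35 h | 62.2% | 38.7% | 0.9% |
| 66 h | 77.7% | 60.4% | 8.0% |

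**3. Level after IV dosing.** Trough/Cavg = kτe^(-kτ)/(1 - e^(-kτ)), with k = ln 2/half-life and τ = 24 h. At 30 h, kτ = 0.5545 and the ratio is 0.5545 × 0.574/0.426 = 0.748. The 48 h level is the trough times the 24 h share from step 2.

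| Half-life | Ratio | Cavg 1500: 24 h / 48 h (ng/mL) | Cavg 500: 24 h / 48 h (ng/mL) |
|---|---|---|---|
| 20 h | 0.641 | 962 / 419 | 321 / 140 |
| 30 h | 0.748 | 1122 / 645 | 374 / 215 |
| 35 h | 0.781 | 1172 / 728 | 391 / 243 |
| 66 h | 0.879 | 1319 / 1025 | 440 / 342 |

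The 24 h level is by construction the ordinary once-daily trough; flow-chart footnote s samples the trough at about that time. The sponsor's simulation puts Cmin above 500 ng/mL in 93.6% of high-risk subjects (section 4.1.1).

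**4. Level 24 h after oral suspension.** 583 × 0.5^(24/half-life) = 254, 335, 362 and 453 ng/mL at 20, 30, 35 and 66 h.

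**5. Do such levels matter?** The documents give no level below which these drugs are safe. One indication: in the circular's Table 13, posaconazole suspension 100 mg once daily raised simvastatin AUC 10.3-fold. Halving the 200 mg single-dose AUC (4,179 fasted to 15,059 ng·hr/mL with a high-fat meal; circular, Table 9) and dividing by 24 h gives a Cavg of about 87-314 ng/mL for 100 mg daily. This assumes linear PK, and the circular does not state the meal conditions of that interaction study. The 24 h IV levels in step 3 all lie above that range; the oral estimates in step 4 lie within or above it. This is suggestive, not an interaction estimate for this trial.

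**The case against.** A reader might infer that footnote a lets a site give pimozide or a statin 24 h after an infusion during the trial. The documents do not support that. The footnote bars concurrent use, and infusions are 22-26 h apart (section 5.2.2); if 24 h were enough, the ban would be empty for a subject dosed daily. Exclusions 14 and 15 keep out subjects who have to take these drugs, and section 5.8 requires permanent discontinuation of those who come to need one.

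The footnote's last sentence can also be read as saying only when sponsor approval must be obtained, not which way the clock runs. Mention of the treatment period fits study drug restarting after inadvertent use of a listed drug or after a short gap; section 5.8 discontinues only when "The subject interrupts trial medication administration for more than 3 consecutive days". Finally, a subject past the last dose is arguably outside footnote a altogether, and the Investigator's Brochure, which is not available here, may give guidance on stopping.

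Most of this stands, and it confines the point to the period after the last dose. It does not fill the gap there: if the waits do not run from posaconazole, the protocol is silent; if they do, they are too short to reflect posaconazole's own elimination.

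**Conclusion.** The concern holds as a minor, cheap improvement for subject safety. Footnote a is ambiguous about direction, and I found no stated interval from the last posaconazole dose to a contraindicated CYP3A4 substrate. If Table 1's figures are borrowed, 57-62% of posaconazole remains at 24 h and 33-39% at 48 h at the two central half-lives. It would be too strong to say that over half always remains at 24 h: that needs a half-life above 24 h, and at 20 h the share is 43%. The 10-day astemizole wait is not open to this criticism to the same degree.

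The number of subjects is not given and is likely small: those stopped under 5.8 because they need such a drug, and those resuming a CYP3A4 statin. The calculation rests on one-compartment decline and on applying the oral circular's half-lives after IV dosing. It measures residual drug, not the risk of an event. No PK endpoint is affected.

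**What to change.** State in footnote a that the listed times run from the prohibited drug to study drug. Add to it, with a cross-reference in the section 5.8 bullet:

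> After the last dose of study drug (IV or oral), do not start astemizole, cisapride, ebastine, halofantrine, pimozide, quinidine, terfenadine, an ergot alkaloid or a statin metabolised via CYP3A4 for 10 days; an earlier start needs consultation with and approval by the sponsor.

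Astemizole has to be in this list, because once the Table 1 times run one way only, its 10 days there would not cover use after posaconazole. The remaining Table 1 rows and footnote b can stay as they are.

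Ten days is the protocol's own posaconazole washout at entry. It is a practical figure and not a proven safe interval: at a 66 h half-life about 8% still remains. The cost is two sentences and a cross-reference. The downside is that an earlier start requires sponsor contact, a route footnote a already provides. Statins not metabolised via CYP3A4 stay unrestricted.

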15. There is any concern by the investigator regarding the safe participation of the subject in the study, or for any other reason, the investigator considers the subject inappropriate for participation in the study. Subject has had any condition that, in the opinion of the investigator, may interfere with optimal participation in the study, i.e., any condition requiring the use of prohibited drugs or unstable medical conditions other than the hematological disorder such as cardiac or neurologic disorder or impairment expected to be unstable or progressive during the course of this study (e.g., seizures or demyelinating syndromes, acute myocardial infarction within 3 months of study entry, myocardial ischemia, or unstable congestive heart failure, unstable arrhythmias, atrial fibrillation with ventricular rate <60/min, or history of torsades de pointes, symptomatic ventricular or sustained arrhythmias, unstable electrolyte abnormalities [e.g., \geq Grade 2 hypokalaemia or hypomagnesaemia]).
16. Subject has had prior enrollment in this study, or other POS studies within 90 days of study entry.
17. Subject has had an Eastern Cooperative Oncology Group (ECOG) [9] performance status >2 prior to induction chemotherapy for the subject's underlying disease.

18. Subject has had a creatinine clearance level (measured or calculated) below 50 mL/min based on the Cockcroft-Gault equation; the Cockcroft-Gault equation is as follows:

$$\text{ClCr} = (140 - \text{age[yr]})(\text{body wt [kg]}) * (0.85 \text{ if female}) \\ (72)(\text{serum creatinine [mg/dL]})$$

When creatinine is measured in micromole/litre, use the following formula:

$$\text{ClCr} = (140 - \text{age[yr]})(\text{body wt[kg]}) * (0.85 \text{ if female}) \\ (72)(\text{serum creatinine [micromol/L]} \times 0.0113)$$

19. Subject has known or suspected Gilbert's disease.

20. Subject is or has an immediate family member (e.g., spouse, parent/legal guardian, sibling or child) who is investigational site or sponsor staff directly involved with this trial.

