
m. The study medication diary will be distributed to subjects when they receive oral suspension treatment and return to investigator at the visit of last dose. Medication and food information during the POS oral suspension dosing period will be collected daily as indicated in the study medication diary.
 
n. Infusion site examination will be performed prior to dosing (0 hour) and at the end of infusion on infusion days and, if applicable, on days where IV Treatment is substituted for Oral Treatment due to oral tolerability issues during the Oral Treatment Phase for local adverse reactions. During the Oral Treatment Phase, any abnormal POS IV infusion site will continue to be inspected at all visits until resolution of the reaction and/or until Day 28 or EOT, which occur first. The infusion site will be monitored for the presence of local site reactions such as, but not limited to, tenderness, erythema, swelling, induration, or frank vein thrombosis. A record of the presence and severity of any reactions, if they occur, is to be obtained.
 
o. Catheter use details will be recorded daily during the IV administration and until 5 days after the end of IV therapy. Catheter type, catheter location (peripheral or central), catheter insertion and removal days, as well as the reason for the removal, will be recorded. For subject switched to oral treatment during Day 11 (±1) to Day 28 or EOT, catheter use could be not needed.
 
p. Clinical laboratory tests should be drawn prior to initiation of study treatment. If the results during screening period are within 72 hours prior medication, the results could also be accepted as Day 1 results. The results of laboratory tests should be documented. The female subject must have a negative serum beta-hCG result prior to study medication.
 
q. If results of these tests obtained within 3 months before screening are available, they can be used as screening.
 
r. Informed consent for future biomedical research testing must be provided before the DNA sample is obtained. The DNA sample should be obtained before the first drug dose on Day 1, or as soon as the informed consent and local regulatory approval for DNA collection and testing are obtained.
 
s. Plasma trough sampling pre-dose on Day 3, 6, 10 (±1), 15 (±1), 22 (±1) and at the end of therapy (or Day 28) for both subgroup 1 and subgroup 2. The trough sample will be taken approx. 24 hours following the previous day's dose of study drug, while before next daily dose. The actual time of all PK samples should be recorded.
 
t. For sub-group 1 subject, Day 10 (±1) blood samples will be collected at pre-dose, 1 hour post start of infusion, immediately before the end of infusion, approximately 15 minutes after the end of infusion, and approximate 4, 8, 12 and 24 hours post start of infusion. Blood for Pharmacokinetic assay of MK-5592 in plasma will be collected within 30 minutes for time points pre-dose, within approximate 1 minute from time points 0-2 hours, within approximate 5 minutes from time points 2-8 hours, within approximate 10 minutes for time points 12 -24 hours, and approximate 30 minutes time points >24 hours.
														

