
7.0 TRIAL PROCEDURES

7.1 Trial Procedures

The Trial Flow Chart - Section 6.0 summarizes the trial procedures to be performed at each visit. Individual trial procedures are described in detail below. It may be necessary to perform these procedures at unscheduled time points if deemed clinically necessary by the investigator.

Furthermore, additional evaluations/testing may be deemed necessary by the investigator and or the Sponsor for reasons related to subject safety. In some cases, such evaluation/testing may be potentially sensitive in nature (e.g., HIV, Hepatitis C, etc.), and thus local regulations may require that additional informed consent be obtained from the subject. In these cases, such evaluations/testing will be performed in accordance with those regulations.

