7.1.1.2 Inclusion/Exclusion Criteria

All inclusion and exclusion criteria will be reviewed by the investigator or qualified designee to ensure that the subject qualifies for the trial.

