7.1.3.1 Laboratory Safety Evaluations (Hematology, Chemistry and Urinalysis)

Laboratory tests for hematology, chemistry and urinalysis are specified in [Table 3](#).

Table 3 Laboratory Tests

Hematology	Chemistry	Urinalysis	Other
Hematocrit	Albumin	Blood	Serum β -human chorionic gonadotropin (β -hCG)
Hemoglobin	Alkaline phosphatase	Glucose	Hepatitis B and C (per site SOP)
Platelet count	Alanine aminotransferase (ALT)	Protein	HIV (per site SOP)
WBC (total and differential)	Aspartate aminotransferase (AST)	Specific gravity	
Absolute Neutrophil Count	Lactate Dehydrogenase (LDH)	Microscopic exam, if abnormal results are noted	
	Calcium		
	Chloride		
	Creatinine		
	Glucose		
	Phosphorus		
	Potassium		
	Sodium		
	Total Bilirubin		
	Direct Bilirubin, if total bilirubin is elevated above the upper limit of normal		
	Total protein		
	Blood Urea Nitrogen (BUN or Urea, BUN is preferred)		

Chemistry laboratory safety tests will be performed after at least an 8-hour fast. Pre-dose laboratory procedures can be conducted up to 24 hours prior to dosing.

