12.4 Approximate Blood/Tissue Volumes Drawn/Collected by Trial Visit and by Sample Types

	Pre-trial	Treatment Periods	Post-trial	Total Collections	mL Per Collection	Total mL/ Test
Laboratory safety tests	1	5		6	10	60
HIV/Hepatitis Screen (at the discretion of the investigator)	1			1	4	4
Blood for Future Biomedical Research		1		1	8.5	8.5
Blood for pregnancy	1	2		3	4	12
Blood for MK-5592 for Sub-group 1 only		13		13	4	52
Blood for MK-5592 for Sub-group 2 only		6		6	4	24
Total Blood Volume Per Subject sub-group 1 /Sub-group 2 [†]						136.5/108.5 mL
[†] If additional pharmacokinetic/pharmacodynamic and/or safety analysis is necessary, additional blood (up to 50 mL) may be obtained. Note: never to exceed 50 mL						

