Subjects Reporting any Adverse Reaction	595 (98)	531 (99)	58 (100)
Body as a Whole - General Disorders			
Fever	274 (45)	254 (47)	32 (55)
Headache	171 (28)	141 (26)	23 (40)
Rigors	122 (20)	87 (16)	17 (29)
Fatigue	101 (17)	98 (18)	5 (9)
Edema Legs	93 (15)	67 (12)	11 (19)
Anorexia	92 (15)	94 (17)	16 (28)
Dizziness	64 (11)	56 (10)	5 (9)
Edema	54 (9)	68 (13)	8 (14)
Weakness	51 (8)	52 (10)	2 (3)
Cardiovascular Disorders, General			
Hypertension	106 (18)	88 (16)	3 (5)
Hypotension	83 (14)	79 (15)	10 (17)
Disorders of Blood and Lymphatic System			
Anemia	149 (25)	124 (23)	16 (28)
Neutropenia	141 (23)	122 (23)	23 (40)
Febrile Neutropenia	118 (20)	85 (16)	23 (40)
Disorders of the Reproductive System and Breast			
Vaginal Hemorrhage*	24 (10)	20 (9)	3 (12)
Gastrointestinal System Disorders			
Diarrhea	256 (42)	212 (39)	35 (60)
Nausea	232 (38)	198 (37)	30 (52)
Vomiting	174 (29)	173 (32)	24 (41)
Abdominal Pain	161 (27)	147 (27)	21 (36)
Constipation	126 (21)	94 (17)	10 (17)
Mucositis NOS	105 (17)	68 (13)	15 (26)
Dyspepsia	61 (10)	50 (9)	6 (10)
Heart Rate and Rhythm Disorders			
Tachycardia	72 (12)	75 (14)	3 (5)
Infection and Infestations			
Bacteremia	107 (18)	98 (18)	16 (28)
Herpes Simplex	88 (15)	61 (11)	10 (17)
Cytomegalovirus Infection	82 (14)	69 (13)	0
Pharyngitis	71 (12)	60 (11)	12 (21)
Upper Respiratory Tract Infection	44 (7)	54 (10)	5 (9)
Liver and Biliary System Disorders			
Bilirubinemia	59 (10)	51 (9)	11 (19)
Metabolic and Nutritional Disorders			
Hypokalemia	181 (30)	142 (26)	30 (52)
Hypomagnesemia	110 (18)	84 (16)	11 (19)
Hyperglycemia	68 (11)	76 (14)	2 (3)
Hypocalcemia	56 (9)	55 (10)	5 (9)
Musculoskeletal System Disorders			
Musculoskeletal Pain	95 (16)	82 (15)	9 (16)
Arthralgia	69 (11)	67 (12)	5 (9)
Back Pain	63 (10)	66 (12)	4 (7)
Platelet, Bleeding and Clotting Disorders			
Thrombocytopenia	175 (29)	146 (27)	20 (34)

Body System Preferred Term	Posaconazole (n=605)	Fluconazole (n=539)	Itraconazole (n=58)
Petechiae	64 (11)	54 (10)	9 (16)
Psychiatric Disorders			
Insomnia	103 (17)	92 (17)	11 (19)
Anxiety	52 (9)	61 (11)	9 (16)
Respiratory System Disorders			
Coughing	146 (24)	130 (24)	14 (24)
Dyspnea	121 (20)	116 (22)	15 (26)
Epistaxis	82 (14)	73 (14)	12 (21)
Skin and Subcutaneous Tissue Disorders			
Rash	113 (19)	96 (18)	25 (43)
Pruritus	69 (11)	62 (12)	11 (19)

* Percentages of sex-specific adverse reactions are based on the number of males/females.
NOS = not otherwise specified.

HIV Infected Subjects with OPC:

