- Concomitant use with medicinal products known to prolong the QTc interval (other than those mentioned in Contraindications).

Electrolyte disturbances, especially those involving potassium, magnesium or calcium levels, should be monitored and corrected as necessary before and during posaconazole therapy.

Posaconazole is an inhibitor of CYP3A4 and should only be used under specific circumstances during treatment with other medicinal products that are metabolised by CYP3A4 (see in Drug interactions).

3. Hepatic Toxicity

Hepatic reactions (e.g., mild to moderate elevations in alanine aminotransferase (ALT), aspartate aminotransferase (AST), alkaline phosphatase, total bilirubin, and/or clinical hepatitis) have been reported in clinical trials. The elevations in liver function tests were generally reversible on discontinuation of therapy, and in some instances these tests normalized without drug interruption and rarely required drug discontinuation. Isolated cases of more severe hepatic reactions including cholestasis or hepatic failure including deaths have been reported in patients with serious underlying

medical conditions (e.g., hematologic malignancy) during treatment with posaconazole. These severe hepatic reactions were seen primarily in subjects receiving the 800 mg daily (400 mg BID or 200 mg QID) in clinical trials.

Liver function tests should be evaluated at the start of and during the course of posaconazole therapy. Patients who develop abnormal liver function tests during posaconazole therapy should be monitored for the development of more severe hepatic injury. Patient management should include laboratory evaluation of hepatic function (particularly liver function tests and bilirubin). Discontinuation of posaconazole must be considered if clinical signs and symptoms consistent with liver disease develop that may be attributable to posaconazole.

4. Use with Midazolam

Concomitant administration of NOXAFIL with midazolam increases the midazolam plasma concentrations by approximately 5 fold. Increased plasma midazolam concentrations could potentiate and prolong hypnotic and sedative effects. Patients must be monitored closely for adverse effects associated with high plasma concentrations of midazolam and benzodiazepine receptor antagonists must be available to reverse these effects.

5. Others

Hypersensitivity

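### Serum magnesium is not in the scheduled laboratory panel, although exclusion 15 uses graded hypomagnesaemia as an example and the appended label names magnesium for monitoring and correction as necessary

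*Combined protocol and SAP*

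**What the plan says.** Section 5.1.3, criterion 15, excludes subjects with conditions that the investigator believes may interfere with participation. Among its bracketed examples are unstable electrolyte abnormalities, illustrated by "Grade 2 hypokalaemia or hypomagnesaemia" (that grade or above). Section 7.1.1.2 adds: "All inclusion and exclusion criteria will be reviewed by the investigator or qualified designee".

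Section 7.1.3.1 fixes the panel: "Laboratory tests for hematology, chemistry and urinalysis are specified in" Table 3. Its chemistry column includes potassium, calcium, sodium, chloride and phosphorus. Magnesium is in no column.

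The flow chart in Section 6.0 schedules chemistry at screening, Day 1, Day 10, Day 15, Day 22 and Day 28/EOT. Footnote p says "Clinical laboratory tests should be drawn prior to initiation of study treatment" and lets a screening result within 72 hours before dosing stand for Day 1. No row or footnote mentions magnesium.

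The oral suspension label in Section 12.10 states: "Electrolyte disturbances, especially those involving potassium, magnesium or calcium levels, should be monitored and corrected as necessary before and during posaconazole therapy". Its adverse reaction table for the pooled prophylaxis studies has a row for "Hypomagnesemia".

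Section 7.1 leaves room for unscheduled work: "additional evaluations/testing may be deemed necessary by the investigator" or the Sponsor, for reasons of subject safety.

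**The concern.** A CTCAE grade for magnesium needs a measured value. The investigator must review every criterion, and the schedule supplies potassium but not magnesium for the example that pairs the two. On treatment, the label names three electrolytes and the schedule covers two of them. Finding low magnesium therefore depends on a site choosing to test for it, and practice may differ across the three or more sites.

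What is at stake is safety monitoring. Magnesium matters here because the label places its electrolyte precaution under arrhythmia and QT prolongation, where it also reports rare torsades de pointes. Safety is the secondary objective, and Section 8.2.2 names laboratory safety tests among the safety endpoints. No planned pharmacokinetic estimate uses magnesium.

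**Working it through.** The point is a missing test, so most of the check is a comparison of the documents.

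**1. Which electrolytes are named, and which are scheduled**

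| Electrolyte | Exclusion 15 example | Label precaution (12.10) | Table 3 chemistry |
|---|---|---|---|
| Potassium | yes | yes | yes |
| Magnesium | yes | yes | **no** |
| Calcium | no | yes | yes |

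Magnesium is one of two electrolytes in the exclusion example and one of three in the label, and it is the only one of them not scheduled.

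**2. Other routes to a result.** The flow chart's laboratory rows are hematology/ANC, urinalysis, chemistry, pregnancy test, HIV/hepatitis screen and blood for future research. None adds magnesium. The out-of-range algorithm in Section 12.5 acts on protocol-specified values, so it cannot prompt a test that the protocol does not specify. That leaves discretionary testing under Section 7.1 and whatever local care measures.

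**3. Planned draws.** The "Laboratory safety tests" row of Section 12.4 gives 1 pre-trial and 5 treatment-period collections:
- 1 + 5 = 6 collections, and 6 x 10 mL = 60 mL, the total printed there.
- The flow chart also gives six chemistry time points, of which four are on drug (Days 10, 15, 22 and 28/EOT).
- Magnesium is in 0 of the 6.

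**4. How common the abnormality is.** From the label's pooled prophylaxis table:
- Hypomagnesemia, posaconazole: 110/605 = 18.2% (Clopper-Pearson 95% CI 15.2% to 21.5%).
- Hypomagnesemia, fluconazole: 84/539 = 15.6%.
- Hypocalcemia, posaconazole: 56/605 = 9.3%. The ratio is 110/56 = 1.96, so the unscheduled abnormality was reported about twice as often as one that is scheduled.

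**5. What those rates can support.** They are treatment-emergent, any-grade rates on oral drug. The 605 subjects are 301 HSCT recipients with GVHD plus 304 with AML/MDS, so about half resemble this trial's population. Mean posaconazole duration was 80 and 29 days respectively:

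(301 x 80 + 304 x 29) / 605 = 32,896 / 605 = 54 days.

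Treatment here lasts at most 28 days and may stop at about 10. The rates show that hypomagnesaemia is common in such patients. They do not give a rate for this trial.

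**6. Size of the change.** 6 x 70 = 420 results at most, or 5 x 70 = 350 if a screening result stands for Day 1 in every subject. Early end of treatment lowers both figures. Screen failures add to them.

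**The case against.** The best case for leaving the plan alone has four parts.

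- **Exclusion 15 is not a laboratory cut-off.** Hypomagnesaemia is an example within an example, under investigator opinion, and other examples there have no dedicated test either. This stands. A reader might infer that the protocol sets a magnesium threshold it cannot enforce; the text does not support that. Even so, an example stated as a grade is of little use without a value.
- **The label has limits.** It says as necessary, sets no panel or timetable, and covers the suspension, which is a study drug only from about Day 11. This also stands. But the precaution speaks of posaconazole therapy, and it names magnesium beside two electrolytes that the protocol does schedule.
- **Other routes exist.** Sites are told to give the suspension under the local label, subjects are inpatients during IV therapy, and extra testing is allowed. These make a magnesium result likelier but do not ensure one.
- **QT protection is already in place.** There are QTc >500 msec entry and stopping rules, Table 1 prohibitions, potassium and calcium testing, ECG monitoring with torsades-risk drugs, and ECGs for every subject at screening, Day -1, Day 1, Day 10 and Day 28/EOT. The label found no mean QTc increase in healthy volunteers. All of this limits the risk. An ECG, however, shows prolongation once present; it does not identify low magnesium as a correctable cause.

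**Conclusion.** The gap is real and specific to magnesium: no magnesium result is scheduled at any of the six chemistry draws. It deserves a change because the remedy is cheap. Its weight is that of a modest safety-monitoring improvement.

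Three stronger readings are tempting and unsupported:
- Applying 18% to 70 subjects would give about 13 cases. The rate is treatment-emergent, any-grade and from longer oral treatment, so it should not become a count here. It says nothing about magnesium at entry, and no Grade 2 or higher rate is given.
- The 18% might be read as a posaconazole effect. The 16% on fluconazole points mainly to a background abnormality to be found and corrected.
- The omission might be taken to leave QT risk unmanaged. The protections listed above still operate.

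The conclusion assumes that Table 3 is the complete panel, as Section 7.1.3.1 presents it. Local practice may already measure magnesium, but the documents do not say so.

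**What to change.** Add serum magnesium to the Table 3 chemistry column at the existing time points: screening, Day 1 (or within 72 hours before dosing, per footnote p), and Days 10, 15, 22 and 28/EOT.

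Once listed, magnesium becomes a protocol-specified value, so Section 12.5 rule B could be read as automatic exclusion for a low result. If a clarifying note is added, it should cover potassium and magnesium alike: exclusion 15 remains an investigator judgement, and a low value may be corrected and repeated before a decision under rule B, which already contemplates a repeat. Rule C is not the right reference, because it covers values that the entry criteria do not mention.

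Cost: one analyte at draws already planned, at most 420 results plus screen failures, and no new visit. Some subjects will need correction and a repeat before the first dose. That the planned 10 mL suffices is an assumption, since Section 12.4 gives no tube or assay detail. The change adds no on-drug result before Day 10, because no chemistry is scheduled between Day 1 and Day 10.
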